5.3.2.5. Exploratory analysis

5.3.2.5.1. Associations between changes in [RAID](#) score and composite disease activity scores (DAS28-ESR^{DD} and CDAI^{DD}).

The first exploratory study objective is to describe the associations between changes in RAID score and composite disease activity scores (DAS28-ESR^{DD} and CDAI^{DD}). Change from baseline in total [RAID](#) score after 24 weeks will be provided using a mixed model repeated measurement. This model includes total [RAID](#) score at baseline and DAS28-ESR^{DD} (respectively CDAI^{DD}) as covariates, and interactions between the covariates and visit. The same model will be used with the CDAI^{DD} instead of DAS28-ESR^{DD}.

SAS code:

```
Proc MIXED;  
Class Visit;  
Model RAID_score_change= DAS28-ESR + Visit + DAS28-ESR*Visit +  
Raid_score_base*Visit;  
Repeated Visit / type=UN sub=id;Run;
```

5.3.2.5.2. Associations between changes in Hospital Anxiety and Depression Scale ([HADS](#)) scores and in composite disease activity scores (DAS28-ESR^{DD} and CDAI^{DD})

The second exploratory study objective is similar to the first. It is to describe the associations between changes in HADS scores and composite disease activity scores (DAS28-ESR^{DD} and CDAI^{DD}). Change from baseline in total [HADS](#) scores after 24 weeks will

¹ Internationally agreed order as defined in table 3-2 of Introductory Guide MedDRA Version 22.1 (available on <https://www.meddra.org/how-to-use/support-documentation/english>)

be provided using a mixed model repeated measurement. This model includes total [HADS](#) score at baseline and DAS28-ESR^{DD} (respectively CDAI^{DD}) as covariates, and interactions between the covariates and visit. The same SAS code will be considered, using HADS scores instead of RAID score for both composite disease activity scores.

5.3.2.5.3. *To explore patients' profiles*

To assess the association between cognitive troubles and patient's characteristics, MATHyS cognition score will be tested. Factors (patient's characteristics) associated with cognitive troubles will be identified using:

- 1 multidimensional analysis (Factorial Analysis for Mixed Data [FAMD])
- 1 logistic regression for cognition score using tertiles (adjacent-category logits model with second tertile as reference)

In a preliminary step, patient's characteristics will be described according to the variable to explain.

FAMD analysis:

This method will allow to establish subjects' profiles, dealing with the small expected number of subjects compared to the high number of variables.

Due to lack of robustness to missing data with this method, subjects with at least one missing value will be excluded from the analysis. Their characteristics (all characteristics listed above) will be described in a summary table.

The FAMD will be conducted as follows:

1. All characteristics and MATHyS cognition score (in 3 classes according to the tertiles) will be entered in the FAMD model.
2. The choice of the number of axes will be determined graphically (percentage of inertia). The raw eigen values histogram will be provided.

Note: As the number of variables impacts the inertia of the analysis (higher number of variables are, higher inertia is).

3. Graphics of variables on factorial axes will be provided to analyse the correlations between variables. Contribution, quality of representation (\cos^2) and v-test will be studied to explain the axes.
4. Graphics of subjects on factorial axes will be provided to analyse the profiles of subjects
5. An Ascending Hierarchical Clustering (AHC) will also be performed after FAMD to create clusters of subjects.
6. A summary table of each cluster will be provided.

Logistic regression analyses:

For the analysis, identification of factors will be conducted in two steps:

1. A univariate analysis of each of the baseline parameter listed above separately. If some factors appear to be associated (i.e., statistically significant at level $\alpha= 0.20$) with outcome, they will be gathered into a multivariate logistic model.
2. A multivariate logistic regression analysis: a stepwise selection of all factors selected in the second step described above, including their interaction, if relevant (significant at $p<0.10$), will be performed. The significance level will be set at 5%.

SAS code (varA is qualitative, varB is quantitative):

```
proc logistic data= table order=data;  
class varA (param=ref ref='reference category');  
model OUTCOME=varA varB /link=logit rsquare maxiter=25;  
run;
```

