### 5.3 EXPLORATORY

- **Over the 6-month core period**
  - To describe the associations between changes in RAID score and composite disease activity scores (DAS28-ESR and CDAI).
  - To describe the associations between changes in HADS score and in composite disease activity scores (DAS28-ESR and CDAI)
  - To explore patient profiles (using multivariate method such as multiple correspondences analysis).
- **Over the long-term extension period (maximum 24 weeks)**

- To assess the safety of sarilumab in combination with csDMARD and/or monotherapy in patients with moderately to severely active RA and inadequate response or intolerance to current csDMARD or TNF inhibitors over the LTE period.

All other analyses that could give interesting information with respect of study objectives will be performed after agreement of the Scientific Committee of the study.

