1.2.3. Exploratory objectives

The exploratory objectives of this study are:

Over the 6-month core period

- To describe the associations between changes in RAID score and composite disease activity scores (DAS28-ESR and CDAI).
- To describe the associations between changes in Hospital Anxiety and Depression Scale (HADS) score and in composite disease activity scores (DAS28-ESR and CDAI)
- To explore patient profiles

Over the long-term extension (LTE) period (maximum 24 weeks)

- To assess the safety of sarilumab in combination with csDMARD and/or monotherapy in patients with moderately to severely active RA and inadequate response or intolerance to current csDMARD or TNF inhibitors over the LTE period. This objective will be considered as a **safety objective** for the rest of the document.

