APPENDIX A: DERIVED DATA

The derived data are variables which are calculated from the raw data in the CRF/eCRF and not included in the database (e.g.: AUC, total score, duration, summary value from repeated observations, study exposure, study drug exposure, study drug cumulative dose, etc.).

The formula used for derived data should be provided and examples may be necessary to clarify the calculation. The strategy for missing data must be specified in the calculation of derived data (e.g.: the minimum number of observations required to calculate an average score, handling incomplete dates).

All references used to calculate the derived data should be mentioned below.

The following derived data will be calculated and included in the listings:

(1) SUBGROUPS DECISION

Treatment started before screening visit and ongoing at screening visit	Prescribed treatment at baseline
csDMARDs	Sarilumab + csDMARDs
Biological therapy	Sarilumab + csDMARDs
csDMARDs or biological therapy	Sarilumab in monotherapy

(2) DAS28-ESR

$DAS28-ESR = 0.56 \times \sqrt{TJC28} + 0.28 \times \sqrt{SJC28} + \ln(ESR) + 0.014 \times PtGA$ (in mm)

Where:

- ln is the natural logarithm
- SJC is the swollen joints
- TJC is the tender joints
- PtGA is the patient's global assessment of disease activity (using a 100 mm VAS)
- ESR is the erythrocyte sedimentation rate (mm/h)

(3) CDAI

$CDAI = TJC28 + SJC28 + PtGA(\text{in cm}) + PhGA(\text{in cm})$

Where:

- SJC is the swollen joints
- TJC is the tender joints
- PhGA is the physician's global assessment of disease activity (using a 100 mm VAS)
- PtGA is the patient's global assessment of disease activity (using a 100 mm VAS)

(4) BMI

BMI (kg/m²) will be derived as $\text{Weight (kg)} / [\text{Height (cm)} / 100]^2$ and rounded to the nearest decimal.

(5) Time between baseline and initial diagnosis (years)

Time between baseline and initial diagnosis in years will be calculated as $(\text{initial diagnosis date} - \text{baseline visit date} + 1) / 365.25$.

(6) Changes from baseline (V2)

Absolute variation (points) from baseline will be calculated as a difference from baseline (e.g. assessment at the visit – assessment at baseline).

Relative variation (%) from baseline will be calculated as: $((\text{assessment at the visit} - \text{assessment at baseline}) / \text{assessment at baseline}) * 100$.

If necessary, evolution will be presented according to decision tables from Appendix B.

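### The model for the association between changes in HADS and changes in DAS28-ESR or CDAI uses the disease-activity score itself, with no change term, no baseline term and no stated visit

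*SAP*

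**What the plan says.** **Objectives.** Protocol 5.3 sets the HADS objective as "To describe the associations between changes in HADS score and in composite disease activity scores (DAS28-ESR and CDAI", and SAP 1.2.3 repeats it ("score and in composite disease activity scores (DAS28-ESR and CDAI"). The headings of SAP 5.1.5.2 and 5.3.2.5.2 use the same construction. The RAID objective in Protocol 5.3 is "To describe the associations between changes in RAID score and composite disease activity scores (DAS28-ESR and CDAI", without the second *in*.

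**Model.** SAP 5.3.2.5.1 fits a repeated-measures mixed model, "Model RAID_score_change= DAS28-ESR + Visit + DAS28-ESR*Visit", with one further term, "Raid_score_base*Visit". CDAI then takes the place of DAS28-ESR. SAP 5.3.2.5.2 opens with "The second exploratory study objective is similar to the first" and closes with "The same SAS code will be considered, using HADS scores instead of RAID score for both composite disease activity scores".

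**Variables.** SAP Appendix A item (2) defines DAS28-ESR as the score and item (3) does the same for CDAI. Change is a separate derived variable, item (6): "Absolute variation (points) from baseline will be calculated as a difference from baseline". SAP 5.3.2.5 does not call on item (6) for DAS28-ESR or CDAI.

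**The concern.** The HADS objective asks whether patients whose disease activity falls also report less anxiety and depression. The model has a change on the left and a score on the right. A patient's score at a visit reflects both where the patient started and how far the patient moved. Without the starting value in the model, one slope carries both.

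The text also leaves open whether the covariate is the baseline or the same-visit value. Two programmers could fit two different models from it, and neither would be change on change. No other analysis in SAP 5.1.5 or 5.3.2.5 relates change to change, so the HADS objective as worded has no analysis that estimates it. At stake is a result reported as an association between changes when it is something else.

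**Working it through.** The documents give no figure for this analysis, so there is none to reproduce. The check compares what each version of the model estimates.

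**Notation.** R0 and D0 are the baseline patient-reported score and baseline disease activity. Dt is disease activity at the visit. ΔR is the change in the patient-reported score, and ΔD = Dt − D0.

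**Target.** ΔR = a + b·R0 + γ·D0 + β·ΔD + error. Here β is the change-on-change slope adjusted for both baselines.

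**Step 1: two equivalent forms.** γ·D0 + β·ΔD = β·Dt + (γ − β)·D0. Same-visit score plus baseline score therefore gives the same β as change plus baseline. A score on the right-hand side is not wrong in itself; what is missing is the baseline (or change) term.

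**Step 2: SAP model read with the same-visit score.** Leaving out D0 gives slope = β + (γ − β)·δ, where δ is the slope of D0 on Dt given R0. With δ positive, the slope is too high when γ > β and too low when γ < β.

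**Step 3: SAP model read with the baseline score.** Leaving out ΔD gives slope = γ + β·κ, where κ is the slope of ΔD on D0 given R0. If patients with higher D0 fall further, κ is negative and the sign can reverse.

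**Step 4: two constructed cases.** The values are assumed: the variance of D0 given R0 is 0.9² = 0.81, and the residual variance of ΔD is 1.2² = 1.44.

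| | Case A | Case B |
|---|---|---|
| β, γ, κ | 0, 0.5, 0 | 0.8, 0, −0.6 |
| δ | 0.81/(0.81 + 1.44) = 0.36 | (0.4 × 0.81)/(0.4² × 0.81 + 1.44) = 0.324/1.5696 = 0.206 |
| Same-visit slope | 0 + 0.5 × 0.36 = 0.18 | 0.8 − 0.8 × 0.206 = 0.63 |
| Baseline slope | 0.5 + 0 = 0.50 | 0 − 0.8 × 0.6 = −0.48 |

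In case A there is no change-on-change link, yet both readings show one. In case B the true slope is 0.80; one reading understates it and the other reverses it. Simulation of one million patients per case agrees to two decimals. In case B, adding D0 to the same-visit model returns 0.80.

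**Step 5: a grid of 108 correlation scenarios, for RAID and DAS28-ESR at one visit.** The only document input is the RAID SD of 2.5 (Protocol 11.1), used at the visit. The rest is assumed:
- SDs: baseline RAID 2.0, baseline DAS28-ESR 1.0, visit DAS28-ESR 1.4.
- Correlations: RAID with DAS28-ESR 0.3–0.5 at baseline and 0.4–0.6 at the visit; baseline with visit 0.3–0.5 for RAID and 0.2–0.5 for DAS28-ESR; cross-lagged 0.1–0.3.

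Results (median, range):
- Change slope adjusted for both baselines: 0.89 (0.45 to 1.59).
- SAP model, same-visit score: 0.78 (0.49 to 1.03). Its ratio to the change slope is 0.96 (0.58 to 1.15).
- SAP model, baseline score: 0.15 (−0.50 to 0.58). It is negative in 42 of 108 scenarios (39%), although the change slope is positive in all of them.
- The two forms in step 1 agree to 4 × 10⁻¹⁶.

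**The case against.** **The RAID objective may match the model.** Read literally, RAID change against the DAS28-ESR or CDAI score is what its wording describes. The SAP's remark on similarity can also be turned round, because the sentence after it in 5.3.2.5.2 restates the HADS objective without the second *in*. This stands as far as RAID is concerned: the wording is ambiguous and a mismatch is not proven. It does not rescue HADS, where Protocol 5.3, SAP 1.2.3 and both section headings agree.

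**Same-visit is the natural reading.** SAP 5.1.5 lists the scores as assessed at each visit, and the code marks baseline RAID with a suffix that DAS28-ESR lacks. That makes the baseline reading less likely. The timing is still unstated, and the same-visit reading still lacks the baseline term.

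**A stronger reading that does not hold.** A reader might infer that the model must weaken the association substantially. With equal variances at both times and a within-patient correlation r of 0.2 to 0.5, change correlates with the week-24 score at √((1 − r)/2) = 0.63 to 0.50, which looks like a loss of 37–50%. That is a marginal correlation, not the slope of a model that adjusts for baseline RAID or HADS. It also rests on an equal-variance assumption that the documents do not give and that the entry criterion of DAS28-ESR above 3.2 makes doubtful. With SDs of 1.0 and 1.4 the correlation is 0.77 to 0.72. In the grid the same-visit slope was below the change slope in about two thirds of scenarios, but the median shortfall was only 4%. The documents support no claim of a sizeable or consistent understatement.

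**Little depends on it.** The objective is exploratory, and Protocol 11.4.2.3 calls all analyses descriptive. This stands and sets the severity.

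**Conclusion.** For HADS the mismatch is clear: the objective is change against change, and the model does not estimate that under either reading of its covariate. For RAID the same correction is sensible because the SAP calls the objectives similar and uses one code for both, but there it resolves an ambiguity and does not correct a proven error.

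The direction of the distortion is not determined by the documents. The ratio of 0.58 to 1.15 and the sign reversal under the baseline reading are illustrations. They rest on assumed SDs and correlations, on RAID with DAS28-ESR, and on complete data at a single visit; the documents give no HADS variability, and the mixed model over several visits will not reproduce them exactly. The algebra in steps 1 to 3 does not depend on those values. Severity is low: no primary or secondary result, sample size or error rate is affected.

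**What to change.** In SAP 5.3.2.5.1 and 5.3.2.5.2, for each of RAID, HADS anxiety and HADS depression, and separately for DAS28-ESR and CDAI:

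- enter the same-visit change from baseline in DAS28-ESR (or CDAI) by visit, and its baseline value by visit. Same-visit score by visit plus baseline score by visit is an equivalent choice, and the slope on the same-visit score is then the one to report;
- keep visit and the baseline RAID or HADS subscore by visit;
- state in words which visit's value each covariate takes;
- state that the RAID objective is read as change against change, or, if the score is intended, say so and name the visit.

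The cost is two model statements and a sentence or two of text. Protocol 9.2.1.2 already makes changes in DAS28-ESR and CDAI secondary endpoints, and SAP Appendix A item (6) already defines change, so no new data are needed.

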### **11.4.2.3 Multiplicity considerations**

Not applicable: all analyses are descriptive without test.

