5.1.5.3. To explore patients' profiles

Patients' profiles will be explored using the same analyses performed for the analysis of baseline data. Association between cognitive troubles and patients' characteristics will be tested. Cognitive troubles will be evaluated by the MATHyS cognition score as qualitative variable (using the tertiles: <1st tertile, [1st tertile; 2nd tertile[, ≥ 2nd tertile).

Characteristics (at baseline) to be tested are:

- Age in quantitative or in classes (using quartiles) if linearity is not verified
- Sex (Female / Male)
- BMI in classes (Normal/Abnormal i.e Underweight or Overweight or Obese)
- Time between baseline and initial diagnosis (years) in quantitative or in classes (using quartiles), if linearity is not verified
- DAS28-ESR in quantitative or in classes (using quartiles), if linearity is not verified
- Patient previously treated with biological therapies and targeted synthetic DMARDs (Yes/No)
- Patient currently treated with corticosteroids for his/her RA (Yes/No)
- Patient currently treated with NSAIDs, analgesics (Yes/No)
- Patient having experienced any past or concomitant diseases (clinically significant) (Yes/No)
- Depression evaluated by HADS (Yes/No). If HADS depression = 'Normal' then Depression='No'. Else if HADS depression = 'Boderline abnormal' or 'Abnormal' then Depression='Yes'
- Anxiety evaluated by HADS (Yes/No). If HADS anxiety = 'Normal' then Anxiety='No'. Else if HADS anxiety = 'Boderline abnormal' or 'Abnormal' then Anxiety='Yes'
- Fatigue (FACIT-F total score) in quantitative or in classes (using quartiles), if linearity is not verified
- Global Assessment of disease activity (mm) by patient (0-no pain to 100-maxima pain imaginable) in quantitative or in classes (using quartiles), if linearity is not verified
- Global Assessment of disease activity (mm) by physician (0-no pain to 100-maxima pain imaginable) in quantitative or in classes (using quartiles), if linearity is not verified
- MATHyS global score in quantitative (only descriptive, not in the model due to collinearity with cognition score)
- Positive Anti-CCP (Yes/No)
- Positive rheumatoid factor (Yes/No)

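### The patient-profile FAMD lets the cognition tertile build the axes and clusters that are then read to show what is associated with cognition

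*SAP*

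**What the plan says.** The exploratory objective on patient profiles (Protocol 5.3, SAP 1.2.3) is carried out in SAP 5.1.5.3 and 5.3.2.5.3.

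- **Purpose.** "Factors (patient's characteristics) associated with cognitive troubles will be identified using" a factor analysis for mixed data (FAMD) and a logistic regression.
- **Outcome.** "Cognitive troubles will be evaluated by the MATHyS cognition score as qualitative variable", in three tertile classes. SAP 5.3.2.5.3 treats it as the dependent quantity: "patient's characteristics will be described according to the variable to explain".
- **FAMD step 1.** "All characteristics and MATHyS cognition score (in 3 classes according to the tertiles) will be entered in the FAMD model". Nothing says that cognition is supplementary (illustrative).
- **Later steps.** The number of axes is chosen graphically. The axes are explained by contributions, cos² and v-tests, and patients are plotted on them. A hierarchical clustering follows the FAMD, and each cluster gets a summary table. Neither the linkage nor the number of clusters is given, and no permutation or other null reference is planned.
- **Characteristics.** SAP 5.1.5.3 lists 17. One of them, the MATHyS global score, is marked "only descriptive, not in the model due to collinearity with cognition score". That leaves 16.

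**The concern.** In a FAMD, every active variable pulls the axes towards itself. If the outcome is active, the axes carry some of its variation by construction, and so do clusters formed on them. The same clusters separate many of the characteristics, because those build the axes too. A reader of the cluster tables then sees groups that differ in cognition and also in, say, disease activity or fatigue, and takes this as association. The pattern can arise with no relation at all between cognition and any characteristic.

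The SAP guards against one form of this problem by keeping the global score out for collinearity with cognition, but it then enters cognition itself. At stake is the credibility of the cognition profiles reported for this objective.

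**Working it through.** The documents give no inertia, error rate or cluster count for this step, so there is no stated figure to reproduce.

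**1. Weight of cognition in the FAMD.** A quantitative variable contributes 1 unit of inertia and a categorical variable with k classes contributes k − 1. Counting the list in SAP 5.1.5.3:

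- 6 quantitative (age, time since diagnosis, DAS28-ESR, FACIT-F, patient and physician global assessments): 6 × 1 = 6
- 10 binary (sex, BMI class, prior biological or targeted therapy, corticosteroids, NSAIDs/analgesics, other diseases, depression, anxiety, anti-CCP, rheumatoid factor): 10 × 1 = 10
- cognition in 3 classes: 3 − 1 = 2

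The total is 6 + 10 + 2 = 18. Cognition supplies 2/18 = 11.1%, and each characteristic 1/18 = 5.6%. SAP 5.1.5.3 allows quartile classes where linearity fails. A variable so coded would carry 3 units; with all six recoded, cognition's share would be 2/(18 + 10 + 2) = 6.7% and it would no longer be the heaviest. The simulations below use quantitative coding.

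**2. Null simulation.** The cognition tertile was generated independently of all 16 characteristics. Sample sizes were 140 (planned) and 112 (= 0.80 × 140), with some runs at 80 because the FAMD uses complete cases only. The FAMD was a singular value decomposition of standardised quantitative columns and scaled indicators. It was followed by Ward clustering on 2, 3, 5 or all axes, cut at 3 or 4 clusters. There were 1,000 datasets per setting (500 with all axes). Characteristics were either mutually independent, or correlated through assumed disease-activity, mood and serology factors.

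Share of datasets in which clusters differ in cognition tertile (chi-square p<0.05):

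| Characteristics | n | Cognition active | Cognition supplementary |
|---|---|---|---|
| Independent | 112 | 87–96% | about 5% |
| Independent | 140 | 90–97% | 4.0–5.8% |
| Correlated | 112 | 46–83% | 4.0–5.6% |
| Correlated (2 axes only) | 140 | 47–52% | 4.1–4.2% |

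For correlated characteristics at n=112, the lowest rate (46.0%) is with 2 axes and 3 clusters, and the highest (83.0%) with all axes and 4 clusters. Further runs with other assumed factor structures gave 41% to 85% for correlated characteristics with cognition active, and 3% to 9% with it supplementary. Rounded, the overall span is 40% to 97% against about 5%.

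**3. Strength on the axes.** With cognition supplementary, the expected null η² per axis is 2/(n − 1) = 2/111 = 0.018 at n=112. The simulated mean over the first two axes was 0.018. With cognition active it was 0.17 (independent) and 0.08 (correlated).

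**4. Apparent factors.** About 10 to 12 of the 16 characteristics differed across clusters whether or not cognition was active, since the clusters are built from them. Clusters differing both in cognition and in at least one characteristic occurred in 88.7% of datasets with cognition active against 4.5% supplementary (n=112, independent, 2 axes, 3 clusters). At n=80 with correlated characteristics the figures were 47.2% against 3.5% (2 axes, 3 clusters) and 69.8% against 5.8% (5 axes, 4 clusters).

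**5. v-tests, which the SAP does plan.** At least one cognition class had |v|>1.96 in 86.5% to 100% of datasets with cognition active, against 22.7% to 51.2% supplementary (n=80 and 112). The supplementary figures reflect only the number of looks. Three classes on 2 axes give 1 − 0.95⁶ = 26.5%, and on 5 axes 1 − 0.95¹⁵ = 53.7%, treating the looks as independent.

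**The case against.** The strongest defence is that a FAMD is a symmetric description of joint structure, that entering every variable is legitimate for that purpose, and that the SAP labels the work exploratory and attaches no cluster-by-cognition test to it. Part of this stands. The chi-square rates measure the distortion; they are not the error rate of a planned test. But the SAP does not present the FAMD as a neutral map. It names a variable to explain and uses the method to identify its associated factors, and its v-tests and cluster tables will be read that way.

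Second, the status of cognition may be settled elsewhere: SAP 5.1.5.3 points to the analyses used for the baseline data, which SAP 7 places in a separate document. That document is not available here. As SAP 5.3.2.5.3 stands, cognition enters alongside the characteristics without distinction. The word active is not used; it is the plain reading.

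Third, the size depends on assumptions. Several characteristics are related: DAS28-ESR contains the patient global assessment by formula, and fatigue, mood and the serology markers may also be correlated. Rates near 90% belong to independent characteristics. Correlated ones give lower rates, though still far above 5%.

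A reader might also infer two stronger points that the documents do not support:

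- **That the reference to all characteristics brings the MATHyS global score into the FAMD.** SAP 5.1.5.3 already keeps that score out of the model, and the natural reading is that this governs.
- **That the logistic regression is circular too, or contradicts Protocol 11.4.2.3** ("Not applicable: all analyses are descriptive without test"). There cognition is the dependent variable, so nothing is circular. Protocol 11.4.2.1 expressly foresees exploratory logistic regression with details left to the SAP. The familiar 1 − 0.95¹⁶ = 56% describes 16 independent single tests, not the planned 0.20 screen followed by stepwise selection.

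**Conclusion.** The concern holds for the FAMD and the clustering that follows it. As written, the outcome helps to construct the axes and clusters used to show what is associated with it. With no true association, clusters would still differ in cognition in roughly 40% to 97% of datasets, against about 5% if cognition were supplementary.

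The direction is secure, because it follows from the construction and appeared in every setting tried. The size is not. It rests on Ward linkage, 3 or 4 clusters, the number of axes retained, quantitative coding of the six continuous characteristics, and the assumed correlation among characteristics. Other linkages and quartile coding were not examined.

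It would be too strong to say that cognition profiles will appear whether or not any exist: the artefact is frequent, not certain. The consequence is misleading cluster tables, plots and v-tests for one exploratory objective. The primary, secondary and safety analyses and the logistic regression are unaffected.

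**What to change.** Reword FAMD step 1 in SAP 5.3.2.5.3 so that:

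1. only the 16 baseline characteristics are active variables;
2. the cognition class is projected afterwards as a supplementary variable, and the MATHyS global score stays out, as SAP 5.1.5.3 already says;
3. the hierarchical clustering is run on the axes from item 1;
4. cognition is then described by cluster.

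If v-tests for the cognition classes are still reported, a permutation reference would account for the several classes and axes inspected. Stating the linkage and the rule for the number of clusters would also close choices now left open.

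The cost is a few lines of SAP text and a change in which variables are declared active. No new data are needed. The downside is that cognition profiles will look less sharply separated.

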(14) **Hospital Anxiety Scale (issue from HADS)**

Total score of anxiety is the sum of tick boxes of columns A (see Appendix D). The range of the total score of anxiety value is 0-21.

(15) **Multidimensional Assessment of Thymic States (MATHys):**

The MATHys is a visual analog scale consisting of 20 items varying from 0 to 10 (see Appendix H). These items corresponded to five dimensions: emotional, cognition, psychomotor function, motivation and sensory perception.

Total score is the sum of the 20 items. The measure is the number of centimetres from the left hand anchor. Items measured from 0 to 10 are: 1; 2; 3; 4; 11; 12; 13; 14; 15; 16; 19; 20 and items measured from 10 to 0 are : 5; 6; 7; 8; 9; 10; 17; 18. A score of 0 corresponds to inhibition of the state evaluated by the item. A score of 5 indicates no change from the patient's usual state and a score of 10 corresponds to excitation for the evaluated state. An overall score of between 0 and 200 is thus obtained. This scale is not devoted to make a diagnosis of mood state but allow to determine the general level of inhibition/activation processes (lower scores indicate general inhibition and higher scores indicate general excitation).

The subscore for **emotional** is obtained by the sum of items: 3; 7; 10; 18. This range is 0 (hyporeactive)-40 (hyperreactive).

The subscore for **cognition** is obtained by the sum of items: 5; 9; 12; 14. This range is 0 (Retardation)-40 (Acceleration).

The subscore for **psychomotor function** is obtained by the sum of items: 2; 11; 19. This range is 0 (Retardation)-30 (Acceleration).

The subscore for **motivation** is obtained by the sum of items: 4; 15; 16; 17. This range is 0 (Decrease)-40 (Increase).

The subscore for **sensory perception** is obtained by the sum of items: 1; 6; 8; 13; 20. This range is 0 (Decrease)-50 (Increase).

See: Chantal Henry, Katia M'Bailara, Flavie Mathieu, Rollon Poinot, Bruno Falissard Construction and validation of a dimensional scale exploring mood disorders: MATHys (Multidimensional Assessment of Thymic States). BMC Psychiatry. 2008; 8: 82.

(16) **Functional Assessment of Chronic Illness Therapy – Fatigue (FACIT-F) per item and total score**

The FACIT measurement system is a comprehensive compilation of questions that measure health related QOL in patients with chronic illnesses. The FACIT-F includes the 13 items.

FACIT-F score is the sum of items, this range is 0 to 52. High FACIT-F scores represent less fatigue.

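### The code given for the cognition-tertile regression fits a different model from the one the SAP text names, and its results depend on how the file is sorted

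*SAP*

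**What the plan says.** SAP 5.1.5.3 sets the outcome of the profile analysis: the MATHyS cognition score in three classes, "using the tertiles: <1st tertile, [1st tertile; 2nd tertile[, ≥ 2nd tertile". SAP Appendix A, item 15, describes the score as running in two directions: "This range is 0 (Retardation)-40 (Acceleration"). On each item, "A score of 5 indicates no change from the patient's usual state".

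SAP 5.3.2.5.3 names the regression as an "adjacent-category logits model with second tertile as reference". The code printed later in that section opens with "proc logistic data= table order=data" and has the model statement "model OUTCOME=varA varB /link=logit rsquare maxiter=25". The factor `varA` has a reference category; OUTCOME has none. No sort step is given. Factors are first screened one at a time at 0.20, then selected stepwise at 5%.

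The same section also plans a factorial analysis of mixed data (FAMD) with clustering, and a description of patient characteristics by outcome class. Both use the tertiles as plain categories.

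**The concern.** The text compares each outer tertile with the middle one. That is a sensible choice for a score with slowing at one end and acceleration at the other, because a factor may be linked to both. The code has no reference tertile. It assumes that a factor shifts patients along one ordered scale by the same odds ratio at every cut, and it takes that scale from whichever tertile happens to occur first, second and third in the file.

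A programmer who follows the code will not fit the model in the text. Two programmers with differently sorted files could report different factors. Nothing in either document reconciles the two specifications.

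**Working it through.** The documents state no figure for this analysis, so there is none to reproduce. I compared the two specifications and then sized the consequence.

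**Inputs**
- Outcome classes: SAP 5.1.5.3. Model, code and thresholds (0.20, then 5%): SAP 5.3.2.5.3.
- N=140 planned (Protocol 11.1, SAP 1.4), with 112 evaluable (Protocol, Clinical Trial Summary) as the lower value.
- Assumptions: one binary factor present in 50% of patients, tertiles of one third each, and the odds ratios (OR) shown below.
- The reading of `link=logit` and `order=data` is standard PROC LOGISTIC behaviour; the documents do not state it.

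**Step 1. The models**
- Text, with separate slopes: log[P(1)/P(2)] = a1 + b1·x and log[P(3)/P(2)] = a3 + b3·x.
- Code: log[P(Y ≤ j)/P(Y > j)] = a_j + b·x for j = 1, 2, with one b and levels ranked by first appearance.
- An adjacent-category model with a common slope would force b1 = −b3, so it could not represent a factor that raises both ends.

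**Step 2. Possible orders**

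Three levels have 3! = 6 orders. The middle tertile stays in the middle in two (1-2-3 and 3-2-1) and comes first or last in four. Reversing an order leaves the cumulative fit unchanged, so 2-1-3 and 1-3-2 represent the four.

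**Step 3. Why order matters**

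*Two-ended factor, OR 3 in both outer tertiles.* Tertile shares are 27.4 / 45.1 / 27.4% without the factor and 39.2 / 21.5 / 39.2% with it. Check: (39.2/21.5)/(27.4/45.1) = 3.0.
- Order 1-2-3, first cut: (39.2/60.8)/(27.4/72.6) = 1.71.
- Order 1-2-3, second cut: (60.8/39.2)/(72.6/27.4) = 0.59 = 1/1.71. The cuts cancel, so the common slope is about zero.
- Order 2-1-3: (21.5/78.5)/(45.1/54.9) = 0.33, then 0.59. Both point the same way, so the factor is seen.

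*One-directional factor, OR 0.5 and 2.* Shares are 44.4 / 33.3 / 22.2% without and 22.2 / 33.3 / 44.4% with it.
- Order 1-2-3: (22.2/77.8)/(44.4/55.6) = 0.36 and (55.6/44.4)/(77.8/22.2) = 0.36.
- Order 2-1-3: (33.3/66.7)/(33.3/66.7) = 1.00, then 0.36. The effect is diluted.

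**Step 4. Simulation**

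There were 1,500 runs per scenario, with likelihood-ratio tests. The table gives the share of runs passing the 0.20 screen at N=140, with N=112 in brackets.

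| OR, tertile 1 v 2 / 3 v 2 | Code, order 1-2-3 | Code, middle tertile first or last | Separate slopes v middle (2 df) |
|---|---|---|---|
| 1 / 1 | 21% (19%) | 20–21% (21–23%) | 20% (21%) |
| 2 / 2 | 21% (21%) | 64–65% (60–61%) | 66% (60%) |
| 3 / 3 | 21% (21%) | 90% (85%) | 93% (87%) |
| 4 / 2 | 65% (56%) | 61–98% (59–96%) | 96% (93%) |
| 0.5 / 2 | 98% (95%) | 63–64% (55–57%) | 95% (91%) |

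At the 5% level, the OR 3 / 3 factor is significant in 6% of runs in order 1-2-3, at either N. With separate slopes it is significant in 77% (N=140) and 67% (N=112).

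The common-slope adjacent-category model passes the OR 3 / 3 factor at 0.20 in 20–21% of runs, no better than the code in order 1-2-3.

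Simulation error is about 1 point: √(0.21·0.79/1500) = 0.011. A repeat at N=140 gave 22% and 91% for the OR 3 / 3 factor, and 64–67% for the diluted one-directional factor.

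**The case against.** The case against has four parts.

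- **The code is a skeleton.** It uses placeholder names and has no selection option, although the text requires stepwise selection. SAP 5.1.5.3 also points to the analyses already done on baseline data, which SAP section 7 places in a separate document. The right model may therefore have been intended, and this stands as a reason not to assume that the wrong one will be run. It does not reconcile the two specifications in this SAP. Nor does reading the code as a template for two binary fits: the text asks for one regression and no subsetting is shown. Even then, with no stated outcome reference, row order would decide which level is modelled.
- **The text is incomplete too.** It does not say that slopes are separate, and with a common slope the named model shares the weakness. This stands, and it shapes the fix.
- **The tertiles are sample tertiles.** The usual state is 5 per item, so 4 × 5 = 20 of 40 on the four-item cognition score. Nothing ensures that the middle tertile contains 20. This stands: the middle tertile is the SAP's chosen comparator, not necessarily the usual state.
- **The stakes are limited.** The objective is exploratory, and the FAMD and descriptive tables are untouched. This stands.

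**Conclusion.** The inconsistency is real. As printed, the code does not fit the model named in the text, and its results depend on row order.

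- **Levels in order 1-2-3 or 3-2-1.** Factors with similar effects at both ends are selected at about the false-positive rate: roughly 21–22% at 0.20 and 5–6% at 0.05 for OR 3 / 3 at N=140, against about 93% and 77% with separate slopes. Unequal two-ended effects are weakened (65% against 96% for OR 4 / 2).
- **Middle tertile first or last.** Two-ended factors can be found, but one-directional ones drop from 98% to about 65% in the OR 0.5 / 2 example.

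These sizes rest on the assumed odds ratios and 50% prevalence. The mechanism in step 3 does not depend on sample size.

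A reader might infer that the code can never detect factors linked to both slowing and acceleration, or that the patient-profile objective as a whole fails. The documents support neither. The first holds only for a monotone level order with roughly equal effects, and the SAP fixes no order. The second ignores the FAMD, the clustering and the descriptive tables. No primary, secondary or safety result is affected.

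**What to change.** In SAP 5.3.2.5.3, replace `link=logit` with `link=glogit`, write the response as OUTCOME(ref='second tertile'), and replace `order=data` with a fixed, stated level order. Add one sentence to the text: slopes are estimated separately for tertile 1 versus 2 and for tertile 3 versus 2. For three levels this equals an adjacent-category model with unequal slopes. Switching to a common-slope adjacent-category link would not solve the problem.

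The cost is a short edit to the code and that sentence; no new data are needed. Each binary or continuous factor then uses two degrees of freedom instead of one. Power for purely monotone effects falls slightly: 95% against 98% at the 0.20 screen in the OR 0.5 / 2 example at N=140.
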